3.2. Justification for Study Design

The number of subjects studied per dose group is expected to be sufficient to meet the study objectives, which are not based on formal statistical hypothesis. Each dose-group will comprise up to 4 subjects (deviations will be allowed). An additional subject will be added if the results from 1 out of 3 subjects are discordant. It is anticipated that 3 dose levels will be sufficient to characterize the exposure-response profile (deviations will be allowed). However, additional cohorts may be studied. A cohort of HD patients may be added to study engagement of pridopidine to S1R and 2D receptors and to explore the effects of neurodegeneration in patients with HD.

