- c. Men who are potentially fertile (not surgically [eg, vasectomy] or congenitally sterile), whose female partners are of childbearing potential, must use contraception for the duration of the study and for 90 days after discontinuation of study drug (because of the possible effects on spermatogenesis). Highly effective methods of

contraception are those with a failure rate of less than 1% per year (eg, female partner's use of hormonal contraceptive [oral, implanted, transdermal, injected], female partner's use of an IUD), and barrier method with spermicide. In addition, male patients may not donate sperm for the duration of the study and for 90 days after discontinuation of study drug.

- d. Body weight ≥ 50 kg.
- e. A sum of ≥ 25 points on the UHDRS-TMS at the screening visit.
- f. Able and willing to provide written informed consent prior to any study related procedure being performed at the screening visit. Patients with a legal guardian should be consented according to local requirements.
- g. Willing to provide a blood sample for genetic analyses (including CAG analysis, CYP2D6 status, S1R polymorphs, genetic long QT syndrome in patients who had QT prolongation following study drug administration or any other genetic analyses related to pridopidine response or HD) at the screening visit.
- h. Willing and able to take oral medication and able to comply with the study specific procedures.
- i. Ambulatory, being able to travel to the study center, and judged by the investigator as likely to be able to continue to travel for the duration of the study.
- j. Availability and willingness of a caregiver, informant or family member to accompany the patient to the clinic at study visits. The suitability of the caregiver should be judged by the investigator.
- k. For patients taking allowed antipsychotic, antidepressant or other psychotropic medication, the dosing of medication must have been kept constant for at least 6 weeks before baseline (visit 2, day -1) and must be kept constant during the study.
- l. Are able to understand the requirements of the study; are willing to comply with the requirements of the study (eg, imaging procedures, all restrictions) and provided their written informed consent to participate in the study.

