- a positive urine drug test or a positive alcohol breath analyzer test at admission visits, or not willing or able to refrain from illicit drugs during the study.

v. Donation or reception of any blood products (eg, plasma, platelets, etc) in the 1 month before the first day of study drug administration, or has made more than 2 donations within the 12 months preceding the first day of study drug administration, or plans to donate during the study or during the 1 months after the last study visit.

w. The subjects cannot participate or successfully complete the study, in the opinion of the investigator, for any of the following reasons:

- The subject is mentally or legally incapacitated, or unable to give consent for any reason.
- The subject is in custody due to an administrative or a legal decision, or under tutelage, or being admitted to a sanitarium or social institution.
- The subject is unable to be contacted in case of emergency.
- The subject is an employee of the site or a relative of an employee at the site.
- Any other reason, at the discretion of the investigator.

Patients with Huntington's disease:

- a. CYP2D6 poor metabolizers
- b. The patient has been previously exposed to ionizing radiation or radioactive substances as a result of clinical research or medical treatment in the past 10 years.
- c. The patient has large scale tattoos, in particular involving the head and neck area.
- d. The patient has a counterindication to having an MRI, including (but not limited to):
 - The presence of metal implants (excluding metal dental crowns) that could affect MRI imaging OR
 - has worked with ferrous metals either as a vocation or hobby (for example sheet metal worker, welder or machinist) in such a way that might have led to unknown indwelling of metal fragments that could cause injury if moved in response to the magnetic fields during the MRI imaging.
- e. The patient suffers from claustrophobia or needle phobia.
- f. The patient has a finding on screening MRI that will, in the opinion of the PI impair the safety of the subject or the scientific integrity of the study.
- g. The patient has a severe motor impairment that might cause artifacts.
- h. The patient has an known coagulation abnormality.
- i. Parts A and 0 only: Individuals who had evidence of only one patent arterial supply to the hand (modified Allen test).

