- p. Patients receiving medications (within the last 6 weeks prior to baseline [visit 2, day -1]) that have been proven to prolong QT interval or who may require such medications during the course of the study such as, but not limited to, non-allowed anti-psychotic medications, tricyclic antidepressants and/or Class I antiarrhythmics.
- q. Patients receiving medications (within the last 6 weeks prior to baseline [visit 2, day -1]) that are metabolized by CYP2D6 and have the potential of reducing seizure threshold.
- r. Creatinine clearance <60 mL/min at screening, calculated using the Cockcroft-Gault equation: $(140 - \text{age}) \times \text{mass (kg)} / 72 \times \text{serum creatinine (mg/dL)}$. It is allowed to repeat the test once, if clinically appropriate.
- s. Any clinically significant, abnormal, screening laboratory result, which in the opinion of the investigator, affects the patients' suitability for the study or puts the patient at risk if he enters the study.
- t. Alcohol and/or drug abuse within the 6 months prior to screening, as defined by [DSM-5 \(American Psychiatric Association 2013\)](#).
- u. Patients with adverse events of suicidal ideation or attempt at any time in the past or as measured by suicide ideation score of ≥ 3 on the C-SSRS (screening version), or patients who answer "Yes" on any of the 5 C-SSRS Suicidal Behavior Items (actual attempt, interrupted attempt, aborted attempt, preparatory acts, or behavior) if the attempt or acts were performed at any time in the past, or patients who, in the opinion of the investigator, present a risk of suicide.
- v. Patients with known intracranial neoplasms, vascular malformations, history of cerebrovascular accident, or intracranial hemorrhage.
- w. Current or history of clinically significant allergy or known hypersensitivity to any ingredients of the study medication [REDACTED]
- x. Treatment with tetrabenazine within 6 weeks of study baseline (visit 2, day -1).
- y. Treatment with any investigational product within 6 weeks of screening prior to the first day of study drug administration or within 5 half-lives (whichever is longer) or

patients planning to participate in another clinical study assessing any investigational product during the study.

z. Use of one of the following prohibited substances, or foods as follows:

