5.3.1. Prohibited Medication for HD Patients

5.3.1.1. Antipsychotic Medication

Ziprasidone, clozapine, haloperidol, mesoridazine, thioridazine, pimozide, zuclopentixol, chlorpromazine, paliperidone, iloperidone, fluphenazine, prochlorperazine, trifluoperazine/trifluoperazine, flupentixol, benperidol, amisulpride, and sulpiride are not allowed within 6 weeks of baseline (visit 2, day -1) and during the study.

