5.3.1.6. Other Prohibited Medications

Due to either QT prolongation effects or metabolism by CYP2D6 into active metabolites, the following medications are not allowed within 6 weeks of baseline (visit 2, day -1) and during the study: astemizole, terfenadine, azithromycin, erythromycin, moxifloxacin, pentamidine, sparfloxacin, clarithromycin, chloroquine, halofantrine, bepridil, cisapride, domperidone, droperidol, levomethadyl, methadone, codeine, tramadol, sevoflurane, and tamoxifene.

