9.1. Sample Size and Power Considerations

This PET study is exploratory in nature; therefore, no formal hypothesis testing is planned. Thus, based on clinical and practical considerations, a sample size of up to approximately 38 subjects (up to 4 subjects per dose level) is considered adequate for this type of study and to attain the study objectives. Up to 45 subjects are planned to be enrolled in this study to ensure up to 38 evaluable subjects. Adaptive study design will allow increasing or reducing the study total sample size or each dose/time cohort as necessary. This sample size may include up to 4 patients with HD, which may be added to study engagement of pridopidine to the D2R and to explore the effects of neurodegeneration.

It is anticipated that 3 dose levels will be sufficient to characterize the exposure-response profile. However, additional cohorts may be studied.

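### Huntington's disease patients on an allowed antipsychotic can enter the Part B D2R scans, where that drug may mimic receptor loss and lower the measured pridopidine occupancy

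*Protocol*

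**What the plan says.** Criterion k for HD patients (Protocol 4.1) reads: "For patients taking allowed antipsychotic, antidepressant or other psychotropic medication, the dosing of medication must have been kept constant for at least 6 weeks" before visit 2, day -1, and the dose may not change during the study. It is not limited to any part. Protocol 4.2 does limit other criteria by part, for example "Parts A and 0 only: Individuals who had evidence of only one patent arterial supply to the hand" (HD exclusion i).

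The limits on antipsychotics are these:

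- Protocol 5.3.1.1 bars 17 named drugs. The list ends "benperidol, amisulpride, and sulpiride are not allowed within 6 weeks of baseline (visit 2, day -1) and during the study". It does not bar the class.
- HD exclusion p covers drugs proven to prolong the "QT interval or who may require such medications during the course of the study such as, but not limited to, non-allowed anti-psychotic" medicines. The word non-allowed implies that others are allowed.
- HD exclusion q removes drugs that are metabolised by CYP2D6 and may lower the seizure threshold.
- HD exclusion x removes "Treatment with tetrabenazine within 6 weeks of study baseline". Protocol 1.1.1 describes that drug as acting on dopamine, but no reason is given for the bar.
- The reason given in 5.3.1.6 is "Due to either QT prolongation effects or metabolism by CYP2D6 into active metabolites". Sections 5.3.1.4 and 5.3.1.5 concern seizure threshold and coagulation.

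Protocol 9.1 allows up to 4 HD patients, "which may be added to study engagement of pridopidine to the D2R and to explore the effects of neurodegeneration". Protocol 3.2 names both receptors: "A cohort of HD patients may be added to study engagement of pridopidine to S1R and 2D receptors". Protocol 1.7 adds the aim of seeing whether the healthy-subject findings recur in patients. Healthy subjects may take nothing but study drug and occasional paracetamol or ibuprofen (5.3). The SAP (7.8) only lists HD patients' medication, and it places the PD and PK/PD analyses outside its scope (10 and 11).

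**The concern.** Protocol 6.2.1.1 defines BP_ND as proportional to the receptors still available to the tracer. A drug already sitting on D2R makes those receptors unavailable. Holding its dose constant keeps its occupancy about equal at the two scans, but does not remove it.

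Two readings are then open to confusion. Baseline BP_ND falls as it would if receptors had been lost, which is the effect of neurodegeneration that HD patients are meant to show. Pridopidine also competes for receptors that are partly taken, so its measured occupancy falls. Healthy comparators carry no such drug, so the distortion lies in the HD group alone. A drug effect could pass for a disease effect or for weaker target engagement in patients.

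That antipsychotics occupy D2R is general pharmacology. The documents do not state it.

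**Working it through.** No figure in the plan bears on this, so there is nothing of its own to reproduce.

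**Inputs**

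- One baseline and one post-dose fallypride scan per subject (Protocol 5.1.3).
- In vitro IC50 of about 10 µM at D2R and about 100 nM at S1R (Protocol 1.1.2), used here as stand-ins for in vivo affinity. This is an assumption.
- f, the D2R fraction occupied by the patient's antipsychotic: not in the documents, so 20, 50 and 80% are assumed.

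**Model.** Let B be drug-free BP_ND without receptor loss (set to 1), L the fraction of receptors lost, A = f/(1-f), and P = RO/(1-RO), where RO is the pridopidine occupancy that would be seen without the antipsychotic. Under reversible competition at one site:

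- Baseline BP_ND = B(1-L)/(1+A) = B(1-L)(1-f)
- Post-dose BP_ND = B(1-L)/(1+A+P)
- Measured RO = P/(1+A+P) = RO(1-f)/(1-f·RO)

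The baseline result also holds if the antipsychotic binds irreversibly. The RO result does not: if the drug simply removed sites, RO would be unchanged.

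**Baseline.** With L = 0, BP_ND reads 0.80, 0.50 and 0.20 at f = 20, 50 and 80%. With one such patient among 4, the mean is (3 + (1-f))/4 = 0.95, 0.875 and 0.80, a fall of 5, 12.5 and 20% with no receptor loss in anyone.

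**Expected D2R occupancy.** At S1R occupancy s, C = 100 nM × s/(1-s), and D2R RO = C/(C + 10,000 nM).

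| S1R occupancy | C (nM) | D2R RO |
|---|---|---|
| 50% | 100 | 1.0% |
| 80% | 400 | 3.8% |
| 90% | 900 | 8.3% |
| 95% | 1,900 | 16.0% |

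**Measured RO**

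| RO without antipsychotic | f = 20% | f = 50% | f = 80% |
|---|---|---|---|
| 8.3% | 6.7% | 4.3% | 1.8% |
| 16.0% | 13.2% | 8.7% | 3.7% |

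For example, at 8.3% and f = 50%: 0.0826 × 0.5/(1 - 0.5 × 0.0826) = 0.0431. In a concentration-RO fit, half-maximal occupancy moves to P = 1 + A, so the apparent EC50 in such a patient is multiplied by 1/(1-f): 1.25, 2 and 5.

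**Can the scans tell drug from disease?** Take two patients:

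- No receptor loss, f = 50%, true RO 8.3% (P = 0.09): baseline 0.500, post-dose 1/(1 + 1 + 0.09) = 0.478.
- No antipsychotic, 50% receptor loss, true RO 4.3%: baseline 0.500, post-dose 0.5 × (1 - 0.0431) = 0.478.

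The data are identical. Each region gives two values for three unknowns (L, f and P), so something from outside the two scans is needed.

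**The case against.** *RO is a within-patient ratio and the dose is constant.* This stands in part. At a D2R occupancy of 8.3% the shift is 1.5, 4.0 or 6.5 points. Test-retest is planned only for fluspidine (9.5.1), so the documents cannot show whether such a shift would be detectable. The ratio is still biased under competition, and baseline BP_ND is not protected at all.

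*The data could be corrected.* A reader might infer that no image analysis could ever recover f. The documents do not support that. Protocol 6.2.1.2 names many regions, and a drug acting throughout the brain would lower all of them whereas regional loss would not. Pridopidine concentration is measured in each patient (3.5), so P could be borrowed from a healthy-subject fit of the 9.7 model. But the first route assumes a spared region, and the second assumes the HD-healthy equivalence that 1.7 wants examined. The second is also imprecise. With P = 0.09 and true f = 0.50, solving f = 1 - [r/(1-r)]/0.09 for a measured RO r of 4.3% with an assumed error of ±2 points gives f anywhere from about 0.25 to 0.74.

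*No baseline comparison is planned.* The stated D2R objectives (2.2.3) are occupancy and its relation to concentration. Interest in neurodegeneration appears in 3.2 and 9.1, not as a D2R endpoint. This limits what is at stake, though both stated objectives use the affected RO.

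*The exposed group may be tiny.* No permitted antipsychotic is named, exclusions p and q are open-ended, and the justification in 4.3 is partly blacked out. All true, and the sponsor's reasoning cannot be judged. Criterion k nevertheless presupposes that some such patients remain.

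*The imaging manual or PK/PD plan may deal with it.* Neither was available. Either could set such patients aside.

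**Conclusion.** The point holds in limited form. Criterion k admits antipsychotic users to Part B, and nothing visible restricts them by binding to D2R. In such a patient baseline BP_ND is reduced by the fraction f. RO is also reduced under reversible competition, by a few points around the 8% D2R occupancy that the in vitro figures suggest at 90% S1R occupancy, and by more if D2R occupancy is higher. The baseline effect is the larger. Its size rests on an assumed f. The (1-f) relation and the need for outside assumptions to separate drug from disease do not.

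Only antipsychotic users in an optional HD cohort of up to 4, under an exploratory objective, are touched. Healthy-subject results are not affected. This is a cheap improvement, not a flaw in the study as a whole.

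A reader might infer that Part A is safe and that criterion k can stay unchanged there. The documents do not support this either. The Protocol's reference list (16) includes a PET study whose title reports high sigma-1 occupancy after a single oral dose of fluvoxamine, and 8.1.2 discusses fluvoxamine in the same context. Criterion k also admits allowed antidepressants, and fluvoxamine is not among those barred in 5.3.1.2, although exclusion q might catch it. S1R occupancy is a primary objective that extends to optional HD patients (2.2.1). The same mechanism could therefore arise in Part A. The documents give no occupancy figure, so its size is not worked out here.

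**What to change.** **Before HD patients enter Part B**, add to the HD exclusions in Protocol 4.2 and in the synopsis:

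> Part B only: any antipsychotic taken in the 6 weeks before visit 2, day -1. Antipsychotic treatment must not be stopped in order to qualify.

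**If HD patients have already been scanned**, add to the imaging or PK/PD analysis plan:

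> Part B HD patients with a drug coded as an antipsychotic (WHO Drug class) at visit 2 or 3 are shown individually. They are left out of any comparison of HD with healthy subjects and of any pooled concentration-RO fit for D2R.

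**For Part A**, treat HD patients on a co-medication that binds S1R in the same way. A drug-class flag will not suffice there, so the sponsor should name the drugs, starting with fluvoxamine, and check whether exclusion q already removes it.

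**Cost.** The Part B exclusion is one sentence and changes no patient's treatment. The flag uses the WHO Drug coding (Protocol 5.3) and the HD medication listing (SAP 7.8) already planned. The Part A list needs a short pharmacology review. The downside is fewer eligible HD patients for a cohort of at most 4, possibly none at a single site, or fewer left in the comparison.

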4.2. Subject Exclusion Criteria

Subjects will not be enrolled in this study if they meet any of the following criteria:

Healthy Subjects:

- a. CYP2D6 poor metabolizers
- b. The subject has been previously exposed to ionizing radiation or radioactive substances as a result of clinical research or medical treatment in the past 10 years.
- c. The subject has large scale tattoos, in particular involving the head and neck area.
- d. The subject has a contraindication to having an MRI, including (but not limited to):
 - The presence of metal implants (excluding metal dental crowns) that could affect MRI imaging OR

- has worked with ferrous metals either as a vocation or hobby (for example sheet metal worker, welder or machinist) in such a way that might have led to unknown indwelling of metal fragments that could cause injury if moved in response to the magnetic fields during the MRI imaging.
- e. The subject suffers from claustrophobia or needle phobia.
- f. The subject has a finding on screening MRI that will, in the opinion of the PI impair the safety of the subject or the scientific integrity of the study.
- g. The subject has a known coagulation abnormality.
- h. Parts A and 0 only: Individuals who had evidence of only one patent arterial supply to the hand (modified Allen test).
- i. Any current or history of heart condition or increased pro-arrhythmic risk, including:
 - History of cardiovascular disease (eg, coronary artery disease, stroke, arrhythmias, congestive heart failure, uncontrolled hypertension, deep vein thrombosis, pulmonary embolism, family history of thrombophilia)
 - History of Long QT Syndrome or a first degree relative with this condition
 - Family history of sudden death/Brugada syndrome
 - A prolonged Fridericia-corrected QT (QTcF) interval (defined as a QTcF interval of >450 msec) at the screening or admission (baseline) visit(s). If there is evidence of a prolonged QTcF interval from the initial (single) measurement, then the ECG can be repeated twice, and the mean of the 3 screening measurements will be used to determine whether or not the subject is suitable for inclusion in the study.
 - Any repolarization deficits
 - Untreated hypokalemia and/or untreated hypomagnesaemia
 - Unclear syncopes
 - Any other clinically significant abnormal ECG as judged by the investigator.
- j. Creatinine clearance <90 mL/min at screening, calculated using the Cockcroft-Gault equation. It is permitted to repeat the test once, if clinically appropriate.
- k. Hemoglobin value below the lower limit of the reference range and evaluated by the investigator to be clinically significant.
- l. Positive serology for HIV-1, HIV-2, HBsAg, and/or hepatitis C.
- m. Presents or has a history of clinically significant diseases of the renal, hepatic, gastrointestinal, cardiovascular, musculoskeletal, immunological, endocrine (including diabetes even if controlled by diet), metabolic diseases, or other condition known to interfere with the absorption, distribution, metabolism or excretion of drugs, as judged by the investigator.

- n. History of alcohol, narcotic, or any other substance dependence in the past 2 years, as defined by the Diagnostic and Statistical Manual of Mental Disorders, Fifth Edition (DSM-5, [American Psychiatric Association 2013](#)).
- o. History of clinically significant psychiatric diseases, such as major depressive disorder or anxiety, as judged by the investigator.
- p. Subjects with adverse events of suicidal ideation or attempt at any time in the past or as measured by suicide ideation score of ≥ 3 on the C-SSRS (screening version), or subjects who answer “Yes” on any of the 5 C-SSRS Suicidal Behavior Items (actual attempt, interrupted attempt, aborted attempt, preparatory acts, or behavior) if the attempt or acts were performed at any time in the past, or subjects who, in the opinion of the investigator, present a risk of suicide.
- q. Has had one of the following conditions:
 - major trauma or surgery in the 2 months before screening or at any time between screening and admission
 - acute/chronic infection within 2 weeks before screening or at any time between screening and admission
 - malignancy within the last 5 years
 - epilepsy, seizure, convulsions or syncope (including febrile seizures)
 - history of tuberculosis
 - BP outside the range of 90 to 139 mmHg (systolic) or 55 to 89 mmHg (diastolic); or pulse rate outside the range of 45 to 99 bpm; all measured after 5 minutes rest in seated or supine position. Vital signs may be retested twice at intervals of 5 minutes.
- r. Not willing or able to refrain from intensive physical exercise during the study.
- s. Current or history of clinically significant allergy or known hypersensitivity to any ingredients of the study medication [REDACTED]
- t. Planned medical treatments (excluding dental care) during the study period, which may interfere with the study.
- u. Use of one of the following prohibited drugs, substances, or foods as follows:
 - an investigational drug (new chemical entity) within 6 weeks prior to the first day of study drug administration or within 5 half-lives (whichever is longer)
 - any monoamine oxidase inhibitors within 14 days before the first day of study drug administration
 - any other medications (including over-the-counter [OTC] medications, vitamins, or herbal or nutritional supplements) within 7 days before the first day of study drug administration (except paracetamol/acetaminophen or ibuprofen used occasionally, up to 24 hours before the first day of study drug administration)

- drugs known to significantly inhibit CYP2D6 enzyme drug metabolism within 21 days prior to the first day of study drug administration or within 5 half-lives (whichever is longer) before the first day of study drug administration, or drugs known to significantly induce CYP enzyme drug metabolism within 28 days before the first day of study drug administration
- drugs known to cause significant QT-prolongation such as anti-arrhythmic drugs or antidepressants within 28 days before the first day of study drug administration
- daily consumption of more than 6 units of caffeine and/or xanthine-containing products, within 2 weeks before the first dose of study drug, or not able to refrain from consumption of more than 2 units of caffeine-containing foods or drinks from 48 hours prior to admission visit and discharge. One caffeine unit is contained in the following items: 1 cup of coffee, 2 cans of cola, 1 cup of tea, $\frac{1}{2}$ cup of energy drink (eg, Red Bull) or 3 chocolate bars. Subject should be able to abstain from caffeine intake for 20 hours during any day.
- cigarette smoking (defined as >5 cigarettes per week) or use of other nicotine-containing products (eg, snuff, nicotine patch, nicotine chewing gum, mock cigarettes, or inhalers). Ex-smokers should have ceased smoking at least 6 months before screening.
- any food or drink/beverage containing alcohol, grapefruit or grapefruit juice, apple or orange juice, vegetables from the mustard green family (eg, kale, broccoli, watercress, collard greens, kohlrabi, brussel sprouts, mustard), and charbroiled meats within 7 days before the first day of study drug administration until after the last day of pharmacokinetic sampling.
- a positive urine drug test or a positive alcohol breath analyzer test at admission visits, or not willing or able to refrain from illicit drugs during the study.

v. Donation or reception of any blood products (eg, plasma, platelets, etc) in the 1 month before the first day of study drug administration, or has made more than 2 donations within the 12 months preceding the first day of study drug administration, or plans to donate during the study or during the 1 months after the last study visit.

w. The subjects cannot participate or successfully complete the study, in the opinion of the investigator, for any of the following reasons:

- The subject is mentally or legally incapacitated, or unable to give consent for any reason.
- The subject is in custody due to an administrative or a legal decision, or under tutelage, or being admitted to a sanitarium or social institution.
- The subject is unable to be contacted in case of emergency.
- The subject is an employee of the site or a relative of an employee at the site.
- Any other reason, at the discretion of the investigator.

Patients with Huntington's disease:

- a. CYP2D6 poor metabolizers
- b. The patient has been previously exposed to ionizing radiation or radioactive substances as a result of clinical research or medical treatment in the past 10 years.
- c. The patient has large scale tattoos, in particular involving the head and neck area.
- d. The patient has a counterindication to having an MRI, including (but not limited to):
 - The presence of metal implants (excluding metal dental crowns) that could affect MRI imaging OR
 - has worked with ferrous metals either as a vocation or hobby (for example sheet metal worker, welder or machinist) in such a way that might have led to unknown indwelling of metal fragments that could cause injury if moved in response to the magnetic fields during the MRI imaging.
- e. The patient suffers from claustrophobia or needle phobia.
- f. The patient has a finding on screening MRI that will, in the opinion of the PI impair the safety of the subject or the scientific integrity of the study.
- g. The patient has a severe motor impairment that might cause artifacts.
- h. The patient has an known coagulation abnormality.
- i. Parts A and 0 only: Individuals who had evidence of only one patent arterial supply to the hand (modified Allen test).
- j. A prolonged QTcF interval (defined as a QTcF interval of >450 msec) at the screening visit. If there is evidence of a prolonged QTcF interval at screening from the initial (single) measurement, then the ECG will be repeated twice, and the mean of the 3 screening measurements will be used to determine whether or not the patient is suitable for inclusion in the study.
- k. Patients with clinically significant heart disease at the screening visit, defined as follows: (i) significant cardiac event (eg, myocardial infarction), angina pectoris or episode of congestive heart failure with symptoms >Grade 2 New York Heart Association classification within 12 weeks before first admission, or presence of cardiac disease that in the opinion of the investigator increased the risk of ventricular arrhythmia, (ii) history of arrhythmia (multifocal premature ventricular contractions, bigeminy, trigeminy, ventricular tachycardia) that was symptomatic or required treatment (Common Terminology Criteria for Adverse Events Grade 3), symptomatic or uncontrolled atrial fibrillation despite treatment, or asymptomatic sustained ventricular tachycardia, (iii) presence of left bundle branch block, (iv) history of deep vein thrombosis or pulmonary embolism, and/or (v) family history of thrombophilia.
- l. Patients with a known history of Long QT Syndrome or a first degree relative with this condition.
- m. Patients with a history of epilepsy or of seizures within the last 5 years.

- n. Have other serious medical illnesses (including but not limited to uncontrolled hypertension, respiratory disease including severe form of asthma, hepatic disease, renal disease, AIDS, unstable psychiatric or other neurologic disorder, endocrine [including controlled diabetes], gastrointestinal, and metabolic diseases) which in the opinion of the investigator may put the patient at risk when participating in the study or may influence the results of the study or affect the patient's ability to take part in the study.
- o. Patients with serum potassium, magnesium and/or calcium levels outside of the central laboratory's reference range at the screening visit and considered clinically significantly abnormal by the investigator. Repeat testing is allowed (up to a maximum of 3 tests) if required to establish whether values are within normal range or clinically significantly abnormal.
- p. Patients receiving medications (within the last 6 weeks prior to baseline [visit 2, day -1]) that have been proven to prolong QT interval or who may require such medications during the course of the study such as, but not limited to, non-allowed anti-psychotic medications, tricyclic antidepressants and/or Class I antiarrhythmics.
- q. Patients receiving medications (within the last 6 weeks prior to baseline [visit 2, day -1]) that are metabolized by CYP2D6 and have the potential of reducing seizure threshold.
- r. Creatinine clearance <60 mL/min at screening, calculated using the Cockcroft-Gault equation: $(140 - \text{age}) \times \text{mass (kg)} / 72 \times \text{serum creatinine (mg/dL)}$. It is allowed to repeat the test once, if clinically appropriate.
- s. Any clinically significant, abnormal, screening laboratory result, which in the opinion of the investigator, affects the patients' suitability for the study or puts the patient at risk if he enters the study.
- t. Alcohol and/or drug abuse within the 6 months prior to screening, as defined by [DSM-5 \(American Psychiatric Association 2013\)](#).
- u. Patients with adverse events of suicidal ideation or attempt at any time in the past or as measured by suicide ideation score of ≥ 3 on the C-SSRS (screening version), or patients who answer "Yes" on any of the 5 C-SSRS Suicidal Behavior Items (actual attempt, interrupted attempt, aborted attempt, preparatory acts, or behavior) if the attempt or acts were performed at any time in the past, or patients who, in the opinion of the investigator, present a risk of suicide.
- v. Patients with known intracranial neoplasms, vascular malformations, history of cerebrovascular accident, or intracranial hemorrhage.
- w. Current or history of clinically significant allergy or known hypersensitivity to any ingredients of the study medication [REDACTED]
- x. Treatment with tetrabenazine within 6 weeks of study baseline (visit 2, day -1).
- y. Treatment with any investigational product within 6 weeks of screening prior to the first day of study drug administration or within 5 half-lives (whichever is longer) or

patients planning to participate in another clinical study assessing any investigational product during the study.

z. Use of one of the following prohibited substances, or foods as follows:

- any food or drink/beverage containing alcohol, grapefruit or grapefruit juice, apple or orange juice, vegetables from the mustard green family (eg, kale, broccoli, watercress, collard greens, kohlrabi, brussel sprouts, mustard), and charbroiled meats within 7 days before the first day of study drug administration until after the last day of pharmacokinetic sampling.
- a positive urine drug test or positive alcohol breath analyzer test at admission visits, or not willing or able to refrain from illicit drugs during the study.

aa. Positive serology for HIV-1, HIV-2, HBsAg, and/or hepatitis C.

